	Post-dose: Drug-related Grade 3 (\geq 160/100 mmHg despite optimal anti-hypertensive treatment)	Dose adjustments of ibrutinib per investigator discretion	Administration of BP lowering therapy should be initiated according to local standard of care. Additional measurements to be performed as clinically indicated until recovery to < 150/90 mmHg. Subsequent study drug administrations maybe reduced by 1 dose level at the investigator's discretion.
Left ventricular systolic dysfunction *Event is considered resolved when the patient is asymptomatic, has a resting ejection fraction \geq 40% and \leq 20% decrease from baseline.	Dose modify/hold copanlisib because of association with cardiac dysfunction. May dose modify/hold ibrutinib as clinically indicated		
	Asymptomatic, resting ejection fraction 40-50%; or 10-20% drop from baseline	Maintain ibrutinib dose per investigator discretion	Maintain copanlisib dose level, and continue with caution Repeat LVEF within 4 weeks or as clinically appropriate
	Symptomatic, responsive to intervention, ejection fraction 20-39% or > 20% drop from baseline	Dose adjustments of ibrutinib per investigator discretion	- Omit copanlisib dose until resolved* (as defined to left), then reduce 1 dose level copanlisib - LVEF measurement to be repeated, if not resolved* within 28 days, permanently discontinue patient from copanlisib treatment
QTc prolongation	Refractory or poorly controlled, ejection fraction < 20%	Discontinue therapy	Discontinue therapy
	Dose modify/hold copanlisib because of association with QTc prolongation. May dose modify/hold ibrutinib as clinically indicated		
	QTc > 500 ms (\geq Grade 3) or > 60 ms change from baseline on at least two separate ECGs	Dose adjustments of ibrutinib per investigator discretion	First Occurrence: - Omit copanlisib dose

			
 - Perform a repeat ECG within one hour of the first QTc of > 500 ms or >60 ms from baseline. Repeat as clinically indicated until QTcF returns to < 480 ms - Seek cardiology input; address electrolytes, correct with supplements as clinically indicated ; review concomitant medication - Once QTc prolongation has resolved, restarted at one lower dose level 
Second Occurrence:
 
 - Off study
Dose modify/hold ibrutinib because of association with atrial fibrillation. May dose modify/hold copanlisib as clinically indicated			
Atrial fibrillation or atrial flutter	Grade 1 or 2	Maintain ibrutinib dose level	Maintain copanlisib dose level
	Grade 3 (Symptomatic and incompletely controlled with medications or device)	Omit ibrutinib dose until resolved to ≤ Grade 1, then resume at reduce 1 dose level Third recurrence: off study	Dose adjustments of copanlisib per investigator discretion
	Grade 4	Discontinue ibrutinib	Discontinue copanlisib
May dose modify/hold copanlisib, ibrutinib or both as clinically indicated			
OTHER CARDIAC DISORDERS	Grade 1 or 2	Omit dose until resolved to ≤ Grade 1, then reduce 1 dose level	
	Grade ≥ 3	Off study	
SKIN	May dose modify/hold copanlisib, ibrutinib, or both based on association with rash		
Rash	Grade 1 (<10% body surface area BSA; no associated erythema or pruritus)	Maintain ibrutinib dose level Consider to initiate appropriate skin toxicity therapy, e.g. with topical corticosteroids B.I.D. and oral antihistamines	Maintain copanlisib dose level
	Grade 2 (10 to 30% BSA and associated with erythema or pruritus; limited instrumental activities of daily living (ADL))	
Tolerable Grade 2:
 
 • Initiate/intensify appropriate skin toxicity therapy, e.g. with topical steroids B.I.D. and oral antihistamines. • Maintain ibrutinib level. 
Intolerable Grade 2 (if considered associated with ibrutinib):
 
 • Omit ibrutinib dose and initiate/intensify appropriate skin toxicity therapy, e.g. with topical steroids B.I.D., oral antihistamines and oral steroids. 
First occurrence:
 
 • If resolved to grade ≤ 1 in ≤ 2 weeks, maintain dose level. • If resolved grade ≤ 1 in more than 2 weeks, ↓ 1 dose level. 	
Tolerable Grade 2:
 
 • Initiate/intensify appropriate skin toxicity therapy, e.g. with topical steroids B.I.D. and oral antihistamines. • Maintain copanlisib level. 
Intolerable Grade 2 (if considered associated with copanlisib):
 
 • First occurrence: Delay infusion until resolved to ≤ Grade 1, maintain dose level • Second and Third occurrence: Delay infusion until resolved to ≤ Grade 1, decrease by one dose level • Fourth occurrence: Discontinue • Start skin directed therapy

		
 Consider continuing skin toxicity therapy up to 2 weeks after re-introduction of ibrutinib. In case of flare after cessation of skin toxicity therapy, consider prompt re-implementation. 
Second occurrence: Omit ibrutinib dose and follow treatment guidance above.
 
 Once resolved to grade ≤ 1, reduce ibrutinib 1 dose level 
According to the investigators discretion, a paired skin biopsy could be obtained (from both an affected and an unaffected skin area for local histopathology assessment) if clinical appropriate.
	
	Grade 3 (Non-macular, papular rash covering $>30\%$ BSA with or without symptoms)	
 Initiate/intensify appropriate skin toxicity therapy, e.g. with topical steroids B.I.D., oral antihistamines and oral steroids. May continue ibrutinib with short term follow up of rash to monitor for improvement If rash does not improve after 5 days on intensified approach, then consider stopping ibrutinib. Once resolved to grade ≤ 1, consider reducing ibrutinib 1 dose level. Consider continuing skin toxicity therapy up to 2 weeks after re-introduction of ibrutinib. In case of flare after cessation of skin toxicity therapy, consider prompt re-implementation. 	
 Initiate/intensify appropriate skin toxicity therapy, e.g. with topical steroids B.I.D., oral antihistamines and oral steroids. May proceed with copanlisib infusion with short term follow up of rash to monitor for improvement If rash does not improve after 5 days on intensified approach, then delay infusion of copanlisib. Consider continuing skin toxicity therapy up to 2 weeks after re-introduction of ibrutinib. In case of flare after cessation of skin toxicity therapy, consider prompt re-implementation. First occurrence: Delay infusion until resolves to \leq Grade 1, decrease by one dose level Second occurrence: Delay infusion until resolves to \leq Grade 1, decrease by one dose level Third occurrence: Discontinue
	Grade 3 (Macules or papules covering $>30\%$ BSA with or without symptoms)	
 Omit ibrutinib dose and initiate/intensify appropriate skin toxicity therapy, e.g. with topical steroids B.I.D., oral antihistamines and oral steroids. Once resolved to grade ≤ 1, reduce ibrutinib 1 dose level. Consider continuing skin toxicity therapy up to 2 weeks after re-introduction of ibrutinib. In case of flare after cessation of skin toxicity therapy, consider prompt re-implementation. 	First occurrence: Delay infusion until resolves to \leq Grade 1, decrease by one dose level Second occurrence: Delay infusion until resolves to \leq Grade 1, decrease by one dose level Third occurrence: Discontinue

		According to the investigators discretion, a paired skin biopsy could be obtained (from both an affected and an unaffected skin area for local histopathology assessment) if clinical appropriate.	
	Grade 4 (including other skin toxicity than maculo-papular rash)	Discontinue ibrutinib According to the investigators discretion, a paired skin biopsy could be obtained (from both an affected and an unaffected skin area for local histopathology assessment) if clinical appropriate.	Discontinue copanlisib
GENERAL	May dose modify/hold copanlisib, ibrutinib or both as clinically indicated		
Fatigue	Grade 1 or 2	Maintain dose level	
	Grade 3	Omit dose until resolves to ≤ Grade 1, then: If resolved ≤ 7 days, then maintain dose level If resolved > 7 days, then reduce 1 dose level	
	Grade 4	Discontinue therapy	
OTHER NON-HEMATOLOGIC EVENTS	May dose modify/hold copanlisib, ibrutinib or both as clinically indicated		
	Grade 1 or 2	Maintain dose level	
	Grade 3	Omit dose If resolved ≤ 7 days, then maintain dose level If resolved > 7 days, then reduce 1 dose level	
	Grade 4	Discontinue therapy	

Note: The investigator may remove any patient from the study for any toxicity, if investigator believes that it is in the best interest of the patient.
 
Note: The investigator may dose reduce either ibrutinib or copanlisib. In situations where toxicities are associated with one drug, the investigator must hold and reduce drug associated with toxicity. The second drug may be continued or modified at the investigator's discretion.
 
Note: If any one drug is permanently discontinued, the patient will be taken off study unless in exceptional situations i.e. if the patient is clearly benefiting from the study treatment (i.e. stable disease or better) and in the opinion of the investigator no safety concerns are present, the patient may remain on the study treatment.
			

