Ibrutinib will be administered once daily continuously until disease progression, intolerance, or completion of 36 cycles, not exceeding 36 cycles since start of therapy whichever comes first. Patients will be instructed to take 420 mg or 560 mg depending on the treating cohort.

Ibrutinib should be administered at about the same time each day orally with 8 ounces or approximately 240 mL of water. The drug should be swallowed intact and subjects should not attempt to crush dissolve the tablets in water. If a dose is missed, the dose may be taken as soon as possible on the same day with a return to the normal schedule the following day. Extra tablets of ibrutinib should not be taken to make up for the missed dose. If a patient vomits the dose, the dose should not be retaken. On days when patients are receiving copanlisib and ibrutinib, patients should take their dose of ibrutinib in clinic just prior to the copanlisib infusion.

9.2. Definitions of dose limiting toxicity, maximum tolerated dose, and recommended phase II dose

A dose limiting toxicity (DLT) is defined as any of the following adverse events occurring within cycle 1 (28 days). A maximum tolerated dose (MTD) is defined as the highest dose studied for which the incidence of DLT is less than 33%. The recommended phase II dose (RP2D) is the dose with clinical efficacy without major toxicity.

- Any AE resulting in a dose delay of >7 consecutive days within the DLT period based on dose modifications in Table 9-6
- Non hematologic AE:
 - Hemorrhage requiring transfusion or procedural intervention, intracranial hemorrhage, intraocular hemorrhage of any grade
 - Grade 4 arterial hypertension
 - Any Grade ≥ 3 AE EXCEPT noted below
 - Grade ≥ 3 nausea, vomiting, constipation or diarrhea persisting for <48 hours
 - Grade ≥ 3 rash or skin hypersensitivity persisting for <7 days
 - <7 days of Grade ≥ 3 fatigue
 - <7 days of Grade ≥ 3 edema
 - <7 days of post infusion blood glucose >250 mg/dL despite optimal glucose management or <2 days of blood glucose >500 mg/dL despite optimal glucose management

- Grade 3 (or 4) isolated electrolyte abnormalities that resolve, with or without intervention, to Grade \leq 2 in less than 72 hours Hematologic AE
 - Any Grade 4 neutropenia lasting more than 7 consecutive days
 - Febrile neutropenia \geq Grade 3 (ANC $<1000/\text{mm}^3$ with a single temperature of $>38.3^\circ\text{C}$ or a sustained temperature of $\geq 38^\circ\text{C}$ for more than 1 hour

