9.7. Dose Continuation, Modification and Interruption

Subjects will be evaluated for AEs at each visit with the NCI CTCAE v5.0 used as a guide for the grading of severity. Prior to completion of cycle 1 in both dose escalation or dose expansion phase, treatment with either ibrutinib, copanlisib or both may be interrupted for \leq 7 days for any reason and then resumed at the same dose. If patients take less than 2 infusions of copanlisib or less than 14 days of ibrutinib during the intended dose of cycle 1, they will be excluded from the DLT analysis and replaced. However if a patient takes less than 14 days of the intended dose of cycle 1 due to a DLT, they will be included in the DLT analysis and not replaced. After completion of cycle 1, study drugs (either ibrutinib, copanlisib) may be interrupted for \leq 28 days for any reason and then resumed at same or reduced dose. The investigator may remove any patient from study for any toxicity if the investigator believes it is in the best interest of the patient to discontinue study treatment.

Intrapatient dose reduction will not be allowed during cycle 1 unless a DLT has occurred and been counted. This is in order to accurately determine the safe and tolerable dose of copanlisib when used in combination with ibrutinib. Dose reductions may be made to ibrutinib and/or copanlisib during cycles 2 and beyond. If a toxicity can be ascribed to a specific study drug, then that drug may be dose modified while the non-offending drug may be maintained. Whether to dose modify ibrutinib or copanlisib is at the discretion of the treating physician.

If the patient experiences unacceptable toxicity that fails to resolve after a maximum dose delay of 28 consecutive days, then the patient should be discontinued from the study treatments. In cases of treatment delays from reactivation of CMV, treatment delays can be extended for up to 2 months. In exceptional situations, if the patient is clearly benefiting from the study treatment (i.e. stable disease or better) and in the opinion of the investigator no safety concerns are present, the patient may remain on the study treatment. Patients who discontinue from study for a study related adverse event or an abnormal laboratory value must be followed as described in Section 10.

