14.0 BIOSTATISTICS

14.1. Phase I

In the Phase I part the standard 3+3 dose escalation scheme will be used. If none of the initial cohort of 3 has a DLT (defined in Section 9.2) the dose level will be escalated. If one has a DLT that dose level will be expanded with 3 more patients. Dose escalation will stop if 2 or more DLTs are seen at a dose level within the treatment and observation periods as described in Section 9.2. The MTD is defined as the highest dose level at which at most 1 of the 6 patients treated at that level has a DLT. Two dose levels plus a "-1" dose level are planned for this study. The maximum sample size is 18 patients. Toxicity seen after 4 weeks that are likely or definitely related to treatment with study drugs will be collected and evaluated by the investigators.

All patients that stop protocol therapy or have dose reductions due to a DLT will be included in the DLT analysis. If a patient stopped therapy for other reasons and has taken $\leq 75\%$ of planned doses (2 of 3 copanlisib doses and 21 of 28 doses of ibrutinib) in the first cycle then they will be excluded from DLT analysis. In the event that a patient withdraws from the trial due to a reason unrelated to a DLT before completing cycle one, they will be replaced. We expect that less than 10% of patients will be replaced due to insufficient time of treatment. The probability of dose escalation based on various underlying DLT rates (Table 2).

Table 14-1. DLT probability table								
True DLT rate	5%	10%	15%	20%	25%	30%	40%	50%
Probability of escalation	0.97	0.91	0.81	0.71	0.60	0.49	0.31	0.17

It is expected that 2-3 patients will be enrolled per month and so the phase I portion of the trial will be completed in approximately 6 months.

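### Sections 9.7 and 14.1 define DLT evaluability in cycle 1 differently, and the literal wording of 9.7 can drop a patient who had a DLT

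*Combined protocol and SAP*

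**What the plan says.** Section 9.7 sets a minimum exposure for cycle 1: "If patients take less than 2 infusions of copanlisib or less than 14 days of ibrutinib during the intended dose of cycle 1", then "they will be excluded from the DLT analysis and replaced". Its exception reads: "However if a patient takes less than 14 days of the intended dose of cycle 1 due to a DLT, they will be included".

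Section 14.1 starts from DLT patients: "All patients that stop protocol therapy or have dose reductions due to a DLT will be included in the DLT analysis". For a patient who stopped for another reason, the limit is ≤75% "of planned doses (2 of 3 copanlisib doses and 21 of 28 doses of ibrutinib) in the first cycle then they will be excluded" from the DLT analysis. A further sentence covers anyone who "withdraws from the trial due to a reason unrelated to a DLT before completing cycle one, they will be replaced", with no dose threshold. The section expects fewer than 10% of patients to be replaced for insufficient treatment time.

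Two other places bear on the point. Section 9.2 lists as a DLT "Any AE resulting in a dose delay of >7 consecutive days within the DLT period". A note to Table 9-7 in Section 9.7 says that when toxicity is tied to one drug, "The second drug may be continued or modified at the investigator's discretion".

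Section 14.1 cross-refers to Section 9.2 but not to 9.7. Section 9.7 does not cite 14.1. Nothing says which rule governs.

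**The concern.** The two rules differ in the ibrutinib limit (14 or 21), the connector (or / and), the inequality (below / at or below), the trigger (any shortfall / therapy stopped) and the protection given to DLT patients. Three problems follow.

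1. **Who is in the denominator.** A non-DLT stopper with 2 infusions and 14 to 20 ibrutinib days is not excluded by 9.7, but is excluded under three of the four readings of 14.1. A patient with 3 infusions and 10 ibrutinib days is excluded by 9.7 and kept by the literal 14.1.
2. **Excluded and replaced are different sets in 14.1.** A patient who withdraws after 3 infusions and 24 ibrutinib days is replaced but not excluded. Under 9.7 the same patient is neither.
3. **A DLT can be lost.** Suppose an AE holds copanlisib on both Day 8 and Day 15 while ibrutinib continues. The delay exceeds 7 days, so it is a DLT. The patient has 1 infusion and at least 14 ibrutinib days, which 9.7 literally excludes and replaces, because its exception is tied to the 14-day limit.

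DLT counts in cohorts of 3 to 6 decide escalation and the MTD, the phase I primary objective. One patient can settle a cohort. With two rules available in an open-label trial, the choice between them can be made after the outcome is known.

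**Working it through.** **Inputs.** Cycle 1 has 3 copanlisib infusions (Days 1, 8, 15) and 28 daily ibrutinib doses (Section 9.1). The DLT window is 28 days (Section 9.2). The 3+3 rule and Table 14-1 are in Section 14.1.

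**Plan's own figure.** With true DLT rate p, P(escalate) = (1−p)³ + 3p(1−p)²·(1−p)³. At the eight tabulated rates this gives 0.973, 0.906, 0.814, 0.709, 0.600, 0.494, 0.309 and 0.172, which reproduces Table 14-1.

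**Do the rules agree under any reading?** Let c be infusions (0 to 3) and i be ibrutinib days (0 to 28), giving 4 × 29 = 116 pairs. Section 9.7 excludes c<2 or i<14, which is 86 pairs.

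| Reading of 14.1: exclude if | Kept by 9.7, excluded by 14.1 | Excluded by 9.7, kept by 14.1 |
|---|---|---|
| c≤2 and i≤21 (literal) | 8 | 28 |
| c≤2 or i≤21 | 23 | 0 |
| c<2 or i<21 | 14 | 0 |
| c<2 and i<21 | 0 | 44 |

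No row is 0 and 0. The grid includes implausible pairs, so these counts test agreement and do not measure frequency.

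**Realistic path.** Take a patient who stops both drugs after day d with no missed doses and infusions on Days 1, 8 and 15. Section 9.7 excludes d = 1–13. In the table's row order, 14.1 excludes d = 1–14, 1–21, 1–20 and 1–7. The stop days in dispute are therefore day 14 only, days 14–21, days 14–20 and days 8–13.

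**Effect of keeping one partly exposed patient.** Assume a constant DLT hazard over 28 days and no DLT observed after the last dose. The latter is a worst case, since AE follow-up continues. A patient exposed for d days has DLT probability q = 1−(1−p)^(d/28). At p = 0.30, q is 0.163 (d=14), 0.225 (d=20) and 0.235 (d=21). With one such patient in the first three:

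P(escalate) = (1−p)²(1−q) + [2p(1−p)(1−q) + q(1−p)²]·(1−p)³

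| True rate | All fully exposed | d=21 | d=20 | d=14 |
|---|---|---|---|---|
| 30% | 0.494 | 0.525 | 0.529 | 0.558 |
| 40% | 0.309 | 0.341 | 0.346 | 0.377 |

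**Average effect.** If 10% of patients are affected, the mean DLT probability per patient is 0.9p + 0.1q. Putting this in the escalation formula at p = 0.30 gives 0.508 (d=21), 0.510 (d=20) and 0.523 (d=14), against 0.494.

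**Dropped DLT.** Take one DLT in the first three, with the other two patients DLT-free.
- Counted: all three added patients must be DLT-free, so (1−p)³ = 0.343 at 30% and 0.216 at 40%.
- Excluded and replaced: (1−p) + p(1−p)³ = 0.70 + 0.30 × 0.343 = 0.803 at 30%, and 0.60 + 0.40 × 0.216 = 0.686 at 40%.

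**The case against.** The strongest reply is that the rules are ambiguous but compatible. Section 9.7 says who is excluded and never says that everyone else is evaluable, so both rules could be applied together, excluding a patient if either one does. This does not settle the matter, because the combined rule still depends on how 14.1 is read. In the table's row order it excludes 86+8 = 94, 86+23 = 109, 86+14 = 100 or 86+0 = 86 of the 116 pairs. It also leaves replaced and excluded as different sets, and leaves the DLT exception as narrow as before.

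On the lost DLT, the exception does not name ibrutinib and might be meant to cover either drug, and 14.1 plainly intends DLT patients to count. The note to Table 9-7 also sits in material introduced for the expansion phase. The intent is probably clear, but the wording does not secure it. The body of Section 9.7 itself allows either drug alone to be interrupted in cycle 1, so the case does not depend on that note.

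Several limits on size stand:
- On the no-gap path the literal 14.1 differs from 9.7 only at day 14. If the third infusion falls on day 14, inside the ±3-day window, the two coincide on that path.
- On that path the 20-day figure applies only under the two readings joined by or, and the 21-day figure only under c≤2 or i≤21.
- The plan's figure of under 10% covers all replacements for insufficient treatment, so the disputed group is smaller and the 1 to 3 point shift is an upper bound.
- Withdrawing from the trial is not the same as stopping therapy, so the second problem may be an unstated link between the two.
- P(escalate) is not the chance of a wrong MTD. The MTD needs at most 1 DLT in 6, the phase II dose can be adjusted after safety review, and toxicity stopping rules cover both phases.

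**Conclusion.** The concern holds and should be fixed. The two sections give different evaluability rules for the same patients, no reading of 14.1 makes them agree, and the literal words of 9.7 can remove a DLT from the count.

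The practical size is modest. Few patients should be affected, because AE delays over 7 days are already DLTs and the 14.1 threshold covers only patients who stopped. The average shift in escalation probability is at most 1 to 3 points at a true rate of 30%, assuming a constant hazard, no DLT seen after the last dose and 10% of patients affected. A single disputed patient among the first three moves it by 3 to 6 points at 30% (0.525−0.494 to 0.558−0.494). The contrast of 0.343 with 0.803 is conditional on a DLT having occurred and then being dropped, and the documents give no frequency for that. Table 14-1 is correct for fully evaluable cohorts. What is unsettled is which patients make up the 3 or 6.

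**What to change.** Reconcile the two sections into one evaluability definition, fixed before dosing, and have the other section cross-refer to it. It should state:

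- the minimum cycle 1 exposure for each drug, with the inequality spelled out;
- whether a shortfall on either drug, or only on both, excludes a patient;
- whether the rule applies only to patients who stop, or also to those using the permitted interruption of up to 7 days;
- whether excluded and replaced patients are the same set;
- that any patient with a DLT always counts, whichever drug was held.

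The threshold is for the sponsor to choose. The cost is one paragraph of wording and, depending on the threshold, possibly a few more replaced phase I patients.

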Each patient is allowed a maximum of two dose reduction of each study drug. Dose reduction of copanlisib or ibrutinib indicates treatment at the next lower dose of copanlisib or ibrutinib based on Table 9-6. If after treatment interruption, resolution of toxicity, and treatment resumption at same dose, the subject presents with the same toxicity at the same severity, then the next treatment re-

initiation must resume at the next lower dose level irrespective of duration. A patient must discontinue therapy if after therapy is resumed at a lower dose, the same toxicity recurs with the same or worse severity. Copanlisib and ibrutinib dose modification guidelines for specific toxicities are outlined in Table 9-7.

Table 9-6. Intrapatient dose reduction*

Drug	Maximum Dose Levels	Reduction Dose Level 1	Reduction Dose Level 2
Copanlisib	60 mg	45 mg	30 mg
Ibrutinib	560 mg daily	420 mg daily	280 mg daily

*Dose reduction starts from the treating dose.

Dose escalation is allowed after the DLT period for ibrutinib to the FDA approved dose levels of 560 mg. However, patients will only be allowed to escalate to this dose once the DLT evaluation period for Dose Level 1 has passed and the dose will not exceed what has been deemed the MTD in other patients. There will be no intrapatient dose escalation of copanlisib. Once a dose reduction for copanlisib of a patient has occurred, the dose level may not be re-escalated during subsequent treatment cycles.

The sections below describe dose reduction steps for patients enrolled in the expansion phase of the study. For patients in the dose expansion phase, the dose must be held per these guidelines and these dose reduction steps can be followed after cycle 1 and per discussion with the PI. Inability to meet treatment criteria will result in holding the dose. If patients have been dose reduced to dose level -1 and continue to meet dose modification criteria to reduce the dose, they will be removed from study treatment.

Table 9-7. Dose modification guidelines

Toxicity Category	Severity (CTCAE 5.0 Grade)	Dose Modifications for ibrutinib	Dose Modifications for copanlisib
HEMATOLOGIC			

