Anemia	Grade ≥ 3 (Hgb <8 g/dL)	Investigator discretion for ibrutinib dosing	
Delay copanlisib infusion until Hgb resolves to \leq grade 3
 
Dose reduction by 1 dose level lower at the investigator's discretion. If more dose reductions are required than allowed per protocol, discontinue copanlisib permanently. The lowest dose level is 30 mg.

May dose modify/hold either ibrutinib, copanlisib or both as clinically indicated			
Neutropenia	Grade 1 (ANC < LLN - $1.5 \times 10^9/L$) Grade 2 (ANC < $1.5 - 1.0 \times 10^9/L$)	Maintain ibrutinib dose	Maintain copanlisib dose
	Grade ≥ 3 (ANC < $1.0 \times 10^9/L$)	
Delay ibrutinib dose until resolves to \leq Grade 1, then: If resolved \leq 7 days, then maintain dose level If resolved $>$ 7 days, then reduce 1 dose level
 
Growth factor support is allowed after cycle 1.
	
Delay copanlisib infusion until ANC resolves to $<$ grade 3
 
Dose reduction by 1 dose level lower at the investigator's discretion. If more dose reductions are required than allowed per protocol, discontinue copanlisib permanently. The lowest dose level is 30 mg.
 
Growth factor support is allowed after cycle 1.

	Febrile neutropenia ($ANC < 1.0 \times 10^9/L$, with a single temperature of $\geq 38.3^\circ C$ or a sustained temperature of $\geq 38^\circ C$ for more than one hour)	
Delay ibrutinib dose until resolves to \leq Grade 1, then reduce 1 dose level
 
Growth factor support is allowed after cycle 1.
	
Delay copanlisib until febrile neutropenia resolves
 
Dose reduction by 1 dose level lower at the investigator's discretion. If more dose reductions are required than allowed per protocol, discontinue copanlisib permanently. The lowest dose level is 30 mg.
 
Growth factor support is allowed after cycle 1.

May dose modify/hold either ibrutinib, copanlisib or both as clinically indicated			
Thrombocytopenia	Grade 1 (PLT < LLN - $75 \times 10^9/L$) Grade 2 (PLT < $75 - 50 \times 10^9/L$)	Maintain ibrutinib dose	Maintain copanlisib dose
	Grade 3 (PLT < $50-25 \times 10^9/L$)	
Delay ibrutinib dose until resolves to \leq Grade 1, then: If resolved \leq 7 days, then maintain dose level If resolved $>$ 7 days, then reduce 1 dose level
	Delay copanlisib infusion until platelet resolves to $>75k$

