14.2. Phase II

The primary objective for this phase II cohort is to assess the complete response rate based on best response by 6 months of ibrutinib and copanlisib and the secondary objective is to measure the disease control rate (stable disease, partial response, and complete response), overall response rate (partial and complete response), duration of response, progression and event free survival. A Simon mini-max two stage design will be used with the goal to increase by complete response rate based on best response by 6 months from 20% to 40%. In first stage, if 5 or more of 18 patients have responses, then the trial will proceed to stage 2. In stage 2, additional patients are enrolled to make the total sample size 33. If 11 or more responses are observed, then the combination is deemed promising. Accrual will not be held while the initial 18 patients in the first stage are evaluated for the 6-month response endpoint. The one sided type I error rate is 0.05 and the power is 0.80. A total of 33 patients will be enrolled, though patients treated at MTD/RP2D from phase I portion of the study will be included in the phase II analysis. Expected accrual is 2-3 patients per month and so the phase II portion will be completed within a year.

For other secondary objectives, the event free survival and progression free survival rates will be assessed by the Kaplan-Meier estimation. Event free survival is defined from the date of first dose to progression, or death, and any events including treatment discontinuation for adverse events or severe adverse events whichever came first. Progression free survival is defined from the date of first dose to progression or death, whichever came first. The duration of response will also be assessed by Kaplan-Meier method but on a sub-cohort of patients who showed any response.

To protect patients from excessive toxicity of the treatment during the entire treatment period, several stopping rules are implemented during the study based on the maximum total number of treated patients in both phase I and II (45). **Treatment related Grade ≥ 3 Pneumonitis or Colitis:** 10% unacceptable rate, 2.5% acceptable rate. Trial to hold enrollment if ≥ 4 deaths related to treatment at any point during the study. Otherwise, hold enrollment based on number of treated patients.

Number of treated patients	1	14	33	45
Number of Gr ≥ 3 Pneumonitis/Colitis to stop the trial	1	2	3	4

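### Section 9.7 gives conflicting instructions for an expansion-phase patient at the combined 45 mg/420 mg dose who needs another reduction, and whether or when an EFS event is counted depends on which is followed

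*Combined protocol and SAP*

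**What the plan says.** Section 9.7 sets a general allowance: "Each patient is allowed a maximum of two dose reduction of each study drug". It then defines a step: "Dose reduction of copanlisib or ibrutinib indicates treatment at the next lower dose of copanlisib or ibrutinib based on Table 9-6". The rows of Table 9-6 read "Copanlisib 60 mg 45 mg 30 mg" and "Ibrutinib 560 mg daily 420 mg daily 280 mg daily", with the footnote "Dose reduction starts from the treating dose".

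Other text relies on the bottom of the copanlisib ladder. The anemia, neutropenia, thrombocytopenia and bleeding rows of Table 9-7 state: "The lowest dose level is 30 mg". Table 9-8 gives the same 30 mg minimum after Grade 2 pneumonitis. The hypertension guidance in Section 9.8 allows a reduction of one or two levels.

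The paragraph that introduces Table 9-7 concerns the expansion phase. It says: "If patients have been dose reduced to dose level -1 and continue to meet dose modification criteria" for a further reduction, they are taken off study treatment. Dose level -1 is defined only in Table 9-2 (Section 9.3), as copanlisib 45 mg with ibrutinib 420 mg. Section 14.1 uses the same label for that planned cohort.

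Section 14.2 defines EFS as time from first dose to progression, death, or "any events including treatment discontinuation for adverse events or severe adverse events", whichever is first.

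**The concern.** A patient at 45/420 who meets reduction criteria again has a next step under one part of Section 9.7 and must stop under another. These are two explicit instructions for the same patient, so the problem is a contradiction and not a missing detail.

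Stopping treatment for toxicity is itself an EFS event. The same patient with the same toxicity is therefore an event on that date under one instruction and still at risk under the other. If treating physicians resolve the conflict differently, part of the EFS curve reflects which sentence each one followed.

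**Working it through.** The plan gives no figure for this point, so the check is to map doses. Inputs: treating doses from Table 9-2, the ladder from Table 9-6, the maximum of two reductions per drug, and dose level -1 = 45/420.

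For each drug:
- steps available = the smaller of 2 and the number of Table 9-6 doses below the treating dose;
- steps used = the number of steps from the treating dose down to the level -1 dose;
- steps cut off = available minus used.

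| Treating dose | Drug | Available | Used at 45/420 | Cut off by removal |
|---|---|---|---|---|
| 60/560 | copanlisib | 2 | 1 | 2 − 1 = 1 (30 mg) |
| 60/560 | ibrutinib | 2 | 1 | 2 − 1 = 1 (280 mg) |
| 45/560 | copanlisib | 1 | 0 | 1 − 0 = 1 (30 mg) |
| 45/560 | ibrutinib | 2 | 1 | 2 − 1 = 1 (280 mg) |
| 45/420 | copanlisib | 1 | 0 | 1 − 0 = 1, if the sentence applies |
| 45/420 | ibrutinib | 1 | 0 | 1 − 0 = 1, if the sentence applies |

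In the last two rows the patient starts at level -1 and has not been reduced to it, so the removal sentence does not literally apply. The plan does not say whether it is meant to. For the other treating doses the conflict is direct.

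Which reductions reach 45/420:
- From 60/560, copanlisib alone goes 60 → 45 → 30 with ibrutinib at 560. Ibrutinib alone goes 560 → 420 → 280 with copanlisib at 60. Neither path passes through 45/420, so there is no conflict.
- From 60/560, reducing both drugs once gives 45/420. From 45/560, one ibrutinib reduction gives 45/420. Here the rules conflict.
- The literal outcome can depend on order. The path 60/560 → 45/560 → 30/560 → 30/420 never meets level -1. The path 60/560 → 45/560 → 45/420 meets it, and a second copanlisib reduction then triggers removal instead of reaching 30/420.

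Table 9-7 against the removal sentence:
- Grade 3 macular or papular rash lowers ibrutinib one level after resolution, and lowers copanlisib one level at the first occurrence and again at the second, with copanlisib stopped at the third. If both drugs are reduced from 60/560, the first occurrence leads to 45/420 and the second asks for copanlisib 30 mg. The removal sentence would end treatment there.
- The Grade ≥3 creatinine row lowers copanlisib at the second and third occurrences. It therefore also assumes two successive steps, but it discontinues ibrutinib, so it is not itself an example at 45/420.

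Effect on the primary design. With 5 or more of 18 to continue and 11 or more of 33 to succeed, P(success) = Σ over x = 5 to 18 of P(X = x; 18, p) × P(Y ≥ 11 − x; 15, p). This gives 0.0458 at p = 0.20 and 0.801 at p = 0.40, in line with the stated 0.05 and 0.80. No term involves the dose-reduction rule.

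**The case against.** The strongest reply is that the overlap is small and mostly governed by other rules. Much of that stands:

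- Dose level -1 is a pair of doses, and Section 9.7 lets one drug be modified while the other is maintained. A reader might infer that 45 mg or 420 mg alone triggers removal, or that every second reduction is blocked. Table 9-2 does not support this, and single-drug reductions from 60/560 fall outside the conflict.
- The removal sentence sits in expansion-phase text.
- Section 9.7 separately ends therapy when the same toxicity returns at the same or worse severity after a reduction. The conflict therefore arises mainly for a different or milder toxicity. This does not remove it entirely, because the rash and creatinine rows prescribe further decreases on recurrence and so sit awkwardly with that rule too.
- Exceptional-situation clauses in Section 9.7 and in the notes to Table 9-7 let some benefiting patients stay on treatment. They add discretion and do not say which rule governs at 45/420.

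A reader might also infer that a 45 mg starter is denied a second copanlisib reduction that the plan guarantees. It is not guaranteed. Two is a maximum, reductions start from the treating dose, and the 30 mg floor leaves one step.

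Finally, dose level -1 could be loose shorthand for the lowest reduction step, which would remove the conflict. But Table 9-6 calls its columns Reduction Dose Level 1 and 2, and the documents use -1 only for the Table 9-2 cohort. Anyone looking up the term finds 45/420.

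**Conclusion.** The contradiction holds for expansion-phase patients reduced to the combined 45/420 dose, either on both drugs from 60/560 or on ibrutinib from 45/560. One Table 9-6 step per drug is available to them under the two-reductions rule and closed under the removal sentence. The conclusion rests on reading dose level -1 as Table 9-2 defines it.

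The consequence is whether the patient stops treatment and so whether, or when, an EFS event is counted. Its size cannot be computed, because the documents give no rate of second reductions. Two stronger conclusions are tempting and are not supported:

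- A percentage-point shift in EFS. One patient is 1/33 = 3.0% of the planned phase II cohort, but multiplying that by an assumed number of patients does not estimate a Kaplan-Meier difference. It names no time point, ignores censoring, and assumes each removed patient would otherwise have stayed event-free.
- A change in how PFS is counted. Section 14.2 defines PFS by progression or death from first dose, and time on treatment is not part of it. Any effect of altered exposure on PFS or on CR by 6 months is conjecture.

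EFS is a secondary endpoint, and the primary analysis is arithmetically untouched. The point still deserves correction, because it governs when patients stop treatment and feeds directly into a named endpoint.

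**What to change.** Reconcile four items in Sections 9.7 and 9.8 into one rule: the two-reductions sentence, Table 9-6, the 30 mg floor in Tables 9-7 and 9-8, and the removal-at-level -1 sentence. State the rule for each possible treating dose (60/560, 45/560, 45/420) and separately for single-drug and combined reductions. Check the rash and creatinine rows of Table 9-7 against it and against the same-toxicity recurrence rule. Which rule to adopt is for the investigator and sponsor to decide.

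The cost is a protocol wording amendment. Sample size, Simon boundaries and the EFS definition need no change.
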